14.2.2 Secondary endpoints

- To assess clinical outcome (suppression of reduction of PVCs burden/VT at 3 months F/U)
- To assess safety
- To assess economical outcome (cost reduction per case)

14.3 STATISTICAL ANALYSIS PLAN

Descriptive statistic data with regard to baseline and procedural variables will be reported; continuous variables will be expressed by mean \pm standard deviation or median and interquartile range (25th, 75th percentile), depending on the normality of distribution; categorical variables will be summarized by frequencies and percentages. The outcome of radiofrequency ablation on the entire cohort of patients will be presented in the form of percentage of patients free from symptomatic or documented arrhythmia or with only mild symptoms related to arrhythmia recurrence.

Depending on the severity of symptoms and documentation of tachycardia during follow-up, patients will be divided into two groups (success/recurrence). Baseline characteristics and procedural variables will be compared between these two groups by student t-tests, Mann Whitney U tests, or Fisher's exact test where appropriate in order to identify those variables associated with better mid/long term outcomes. A two-tailed p value <0.05 will be considered statistically significant. Intra-patient improvement from baseline to 6 months follow-up visit will be assessed by McNemar's test. Freedom from PVC/VT will be assessed as a time-dependent variable using Cox proportional hazard models.

To judge if ablation strategy using Vivo mapping system is as successful in achieving the clinical endpoint, we will compare the procedure parameters as well as the outcome of this trial to age & gender matched procedures of the same operator from the last 5 years' database.

To measure the strength of association between the acute successes (PVC/VT suppression at the end of the ablation) and outcome, a McNemar test will be performed. Data will be analyzed using SPSS version 18 (IBM Corporation).

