4.3.2 Procedure Requirements

4.3.2a Prior to EP Procedure

Prior to the procedure the subject will undergo cardiac and thoracic imaging. This can be in the form of a MRI or CT scan, based on physician preference. Specific MRI and CT scan protocols do not significantly differ from the protocols already in use at the Brompton for pre-procedure roadmap scan. The recorded DICOM images should be provided the physician to upload into VIVO for future segmentation. The Mortara 12-lead Holter will be used to record the patient’s PVCs templates (with their respective frequency of presentation). The recorded files will be then imported into Vivo analysis software for the analysis and localization on the pre-reconstructed model. Likewise, the analysis will be done with templates from the Sensis software in the catheter laboratory.

The 3 D Camera will be used to take a 3D image of the patient’s torso after ECG lead placement. This will be merged with the cardiac anatomy from the 3D scan.

4.3.2b During the EP procedure

The EP procedure will be completed per the Institution’s standard of care using a 3D electroanatomical mapping system (CARTO, Biosense Webster).

The information from VIVO analysis will be integrated in the 3D mapping process such that the ablation procedure will be provided with this information, or in post-processing to establish the accuracy of the localization.

Pacing locations can be selected at any time during the procedure based on the physician’s preference.

4.3.2c Registration of EAM to Imaging

Left sided ablations: A Carto mapping catheter will be used to generate a complete fast anatomic map (FAM) anatomic shell of the left ventricle for identification of cardiac structures related to imaging. Imaging should be acquired at End Diastole. Landmarks will include those that are required for the individual procedure, including the papillary muscles if pacing is planned on the papillary muscles.

Right sided ablations: A Carto mapping catheter will be used to generate a complete fast anatomic map of the entire right ventricle and right ventricular outflow tract. Landmarks will include those that are required for the individual procedure.

4.3.2d Identifying the location of PVC or VT Origin

Identification with VIVO: Identifying the location of the PVC or VT foci with VIVO will be done prior to the patient's procedure.

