6. STUDY DESIGN

6.1 OVERALL DESIGN

This is a prospective, single arm, observational and feasibility study, which will recruit 15 non-selected patients, with structurally normal heart, with a conventional indication for catheter ablation of PVCs/VT. The follow up will be of three months. The study will also include another retrospective cohort, including age & gender matched patients, without cardiac structural disease, with a conventional indication for catheter ablation of PVCs/VT from the last 5 years' database of the same operator. For this second retrospective cohort there will be no follow-up.

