10.5 SUMMARY CHART OF STUDY ASSESSMENTS

	Pre-ablation	Pre-discharge	3 months
12 lead ECG		X (routine)	X (routine)
Telemetry	X (routine)		
Contrast CT scan or non-contrast CMR for roadmap	X (routine)		
TTE		x (routine)	
Symptom questionnaire	X (research)		X (research)
Clinic Visit			X (EP OPC)
ECG Holter (Mortara)	X (research)		X (research)

Follow up

3 months
Follow-up visit

RHYTHM & SAFETY
Review therapy, allow Re-ablation if necessary using same methodology
Assess recurrences by 12-lead Mortara Holter

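### Section 14.3 plans no analysis of PVC burden, names an unscheduled 6-month visit instead of the 3-month one, and counts mild-symptom recurrence as favourable, so it does not report the clinical outcome set in 14.2.2

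*Combined protocol and SAP*

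**What the plan says.** **Endpoint.** Section 14.2.2 lists as a secondary endpoint "To assess clinical outcome (suppression of reduction of PVCs burden/VT at 3 months F/U"). The synopsis has the same objective, and section 6.2 justifies the length of follow-up by the effect of ablation on arrhythmia burden.

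**Schedule.** Section 6.1 states "The follow up will be of three months". Section 10.4 makes the 3-month visit the point of study completion and endpoint assessment. The charts in 6.3 and 10.5 place a Mortara Holter before ablation and at 3 months; 10.5 gives the purpose of the later one as "Assess recurrences by 12-lead Mortara Holter". Section 4.3.2a says the pre-procedure recording captures "PVCs templates (with their respective frequency of presentation").

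**Analysis.** Section 14.3 sets out these outcome measures:

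- a whole-cohort "percentage of patients free from symptomatic or documented arrhythmia or with only mild symptoms related to arrhythmia recurrence";
- a success/recurrence split: "Depending on the severity of symptoms and documentation of tachycardia during follow-up, patients will be divided into two groups";
- a McNemar test of "Intra-patient improvement from baseline to 6 months follow-up visit";
- a survival model: "Freedom from PVC/VT will be assessed as a time-dependent variable using Cox proportional hazard models";
- a comparison of the outcome with matched historical procedures, and a McNemar test relating acute success to outcome. Neither says what the outcome is.

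**The concern.** An analyst who follows 14.3 exactly will not produce the result that 14.2.2 promises. The two Holter recordings are never compared, and the reported percentage mixes patients without arrhythmia with patients whose arrhythmia has come back but troubles them little. Symptom tolerance and burden reduction are different outcomes, and the endpoint names burden.

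The gap reaches beyond one percentage. The split drives the comparisons of baseline and procedural variables at two-sided p < 0.05, and the acute-success association needs a defined outcome too. Section 14.1 says the pilot is meant to lead to a powered multicentre trial. Without a burden summary or a reproducible definition of success, it cannot give that trial a usable estimate for the clinical outcome.

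**Working it through.** The plan gives no figure to reproduce: section 14.1 states that no power calculation was done, and no event rate or burden value is given. The check is therefore mainly textual.

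**1. Endpoint terms in 14.3.** A word count of the section gives: *burden* 0, *Holter* 0, *reduction* 0, *3 month*, *3-month* or *three* 0. *Month* occurs once, in the 6-month McNemar sentence. *Suppression* occurs once, for the acute result at the end of ablation. The general descriptive summaries are limited to baseline and procedural variables, so they do not supply a 3-month burden summary either.

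**2. Time point.** The McNemar test refers to a 6-month visit. Sections 6.1, 6.3, 10.4 and 10.5 have no visit after 3 months, so the test as written has no data. Nor does 14.3 say which yes/no variable is paired.

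**3. Two patients followed through the rules.** A: PVC burden fully back at 3 months, mild symptoms, no documented tachycardia. B: burden clearly reduced but some PVCs on Holter, no symptoms, no documented tachycardia.

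| Rule | Patient A | Patient B |
|---|---|---|
| 14.2.2 endpoint (burden) | not met | reduction met |
| 14.3 percentage (*arrhythmia*) | favourable, by the mild-symptom clause | unclear: arrhythmia is documented, and the mild-symptom clause may or may not include no symptoms |
| 14.3 split (*tachycardia*, symptom severity) | undetermined, no severity cut-off | most naturally success |
| 14.3 Cox model (*PVC/VT*) | event | event |

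Patient A is favourable in the percentage although the burden endpoint has failed. Patient B meets the endpoint but is an event in the Cox model. *Mild* is not graded anywhere in 14.3.

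**4. Treatment before 3 months.** Section 6.2 provides for drug changes, DCCV and re-ablation after early recurrence. Section 14.3 does not say whether a patient treated in this way and quiet on the 3-month Holter is a success or a recurrence.

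**5. Size.** n = 15 (section 14.1). One patient is 1/15 = 6.7 percentage points. Illustration with assumed counts: 10 arrhythmia-free patients give 10/15 = 66.7% (exact Clopper-Pearson 95% interval 38.4 to 88.2). Adding 3 mild-symptom recurrences as favourable gives 13/15 = 86.7% (59.5 to 98.3), a shift of 3/15 = 20.0 points. Only n and the 6.7 points per patient come from the plan.

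**The case against.** Several counter-arguments have force.

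- **The three-month window.** A reader might infer that 14.3 contains nothing that covers 3 months. That goes too far. Follow-up is three months and the study ends at the last visit, so the split and the Cox model fall in that window and partly address suppression and VT. The 6-month wording affects one test and may be a slip. What stands is that no analysis names the 3-month visit and none addresses burden reduction.
- **The Holter's purpose.** The pre-ablation recording is made on the ward (10.3) to obtain templates for VIVO localisation, and arrhythmia may be provoked if none appears. It is not clearly a burden measurement, and no recording length is given for either time point. The 3-month Holter can feed documented arrhythmia in 14.3, so it is not wholly unused. This limits how precise a burden analysis can be. It does not excuse having none, because burden is the stated endpoint.
- **Early recurrence.** The split looks at events during follow-up, so a treated, documented tachycardia would naturally be a recurrence there. The silence matters mainly for PVC-only recurrence and for status at 3 months.
- **Effect on significance.** A reader might infer that the mild-symptom clause could push a success/recurrence comparison across p = 0.05. The documents do not support this: 14.3 gives the split no mild-symptom cut-off, and any p value would rest on assumed counts.
- **Descriptive design.** Section 14 calls the design descriptive only. A descriptive plan still needs to describe its endpoint, and 14.3 also sets a significance threshold.

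**Conclusion.** The point holds. Section 14.3 has no analysis of PVC burden or its reduction, its one named visit conflicts with the schedule, and its outcome percentage can count full return of PVC burden as favourable. Different event wording means that one patient may be classified differently by the percentage, the split and the Cox model.

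The size is 6.7 points per mild-symptom recurrence counted as favourable. The number of such patients, and hence the total shift, cannot be known from the documents. The percentage cannot be lower than the strictly arrhythmia-free rate, because the clause only adds patients.

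The consequence is limited to a secondary endpoint in an unpowered 15-patient pilot; the procedure-time comparison is untouched. It should be corrected before the 3-month data are read, but it does not threaten the primary objectives.

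**What to change.** In section 14.3:

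- **Time point.** Change the 6-month McNemar time point to the scheduled 3-month visit and name the paired variable.
- **Burden.** Report paired Holter PVC burden at baseline and 3 months from unprovoked recordings, plus documented VT. State the recording length at each time point and normalise to it, for example PVCs per hour or percentage of beats. Give absolute change, and percentage change only where baseline burden is non-trivial. Describe separately patients with only provoked arrhythmia, or with VT and little PVC burden.
- **Percentage.** Report arrhythmia-free patients and mild-symptom recurrences as separate counts.
- **One definition.** Use a single definition of success/recurrence, chosen by the sponsor and fixed before any 3-month Holter is read, for the percentage, the split and the acute-success association. If the Cox model is kept, give it a matching event.
- **Early treatment.** State whether treatment for early recurrence before the 3-month assessment counts as recurrence, and show the result regardless of such treatment as a sensitivity analysis.

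The cost is mostly wording, because Holter and questionnaire are already scheduled at both time points. The CRF needs fields for recording length, provoked or unprovoked baseline, and date and type of any early treatment. The reported success rate may be lower, and some patients will have no usable baseline burden. If the ward recording is short, the change in burden will be imprecise and should be described as such.

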3. STUDY SYNOPSIS

Full study title:	VIVO™ non-invasive Time Assessment Protocol
Short study title:	VIVO™ mapping Protocol
Study R&D number:	VIVO-RBH01
Chief Investigator:	[name]
Medical condition/disease under investigation:	Patients undergoing PVC/VT Ablation with structurally normal hearts
Study duration:	9 months
Primary Objective:	
Safety:
 
 • Absence of acute adverse events due to the use of VIVO system during PVC/VT ablation • Safety endpoint of the entire mapping and ablation strategy 
Efficacy:
 
 • To assess the efficacy of VIVO to decrease procedure time as compared to standard of care ablation procedures.
Secondary Objective:	
 • To assess clinical outcome (suppression of reduction of PVCs burden/VT at 3-month F/U) • To assess economical outcome (cost reduction per case)
Study population:	
VIVO Cohort – 15 patients presenting for PVC/VT ablation with structurally normal heart
 
Control Cohort – Retrospective review of historical matched patients within the physician's database that had PVC/VT ablations with structurally normal hearts

Recruitment Target	15 patients
Recruitment Window (Months)	6 months
Methodology:	The study is a non-randomized, single-centre, study designed to evaluate the procedural efficacy of VIVO as compared to standard of care ablation procedures. Up to 15 patients will be enrolled.
Eligibility criteria:	
Inclusion criteria:
 
 1. Subjects who are at least 18 years or older 2. Subjects who are scheduled for PVC/VT ablation procedure 3. Subjects who have signed an IRB/EC approved Informed Consent Form and applicable subject privacy protection authorization per local law 4. Subjects will be selected without regard to gender or age (unless precluded by local regulatory requirements) 5. Subjects with or without cardiac structural disease
	
Exclusion criteria:
 
 1. Reversible causes of PVC/VT 2. Subjects with recent (within 3 months) acute coronary syndrome 3. Subjects who are contraindicated for CT or MRI (must be able to get one)

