14. STATISTICAL DESIGN

This is a prospective, non-randomised, observational study which will recruit 15 non-selected patients with PVC/VT eligible for catheter ablation, without structural heart disease.

Procedural outcomes will be compared to age & gender matched procedures of the same operator from the last 5 years' database.

The statistical design was decided in collaboration with the study PIs and will be descriptive only.

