14.1 SAMPLE SIZE AND RECRUITMENT

This is a feasibility pilot study, which will test the feasibility of PVC/VT foci mapping with Vivo system and catheter ablation in unselected patients without structural heart disease, eligible for PVC/VT ablation. Therefore, no power calculation has been done and the number of patient recruited will be of 15 which are deemed sufficient by the CI and Co-PIs on a clinical basis.

The estimated recruitment period for the trial will be of 6 months. We estimate that this sample size is attainable in practice, as the number of PVC/VT ablation procedures per year performed within the Trust is around 100. We also included patients with previous PVC/VT ablation in order to maximise chances of recruitment. This pilot is performed with the intention to plan a prospective multi-operator/multicentre trial which is adequately powered. We will aim to compare the procedure parameters as well as the outcome of this trial to age & gender matched procedures of the same operators from the last 5 years' database.

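### Section 14.3 uses p<0.05 to identify variables associated with outcome among at most 15 patients, although Section 14 declares the design descriptive; associations named this way would generally be unreliable

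*Combined protocol and SAP*

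**What the plan says.** Section 14 describes the statistical design in general terms: it "will be descriptive only". Section 14.1 adds that "no power calculation has been done and the number of patient recruited will be of 15", and the synopsis (Section 3) makes that number a ceiling: "Up to 15 patients will be enrolled".

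Section 14.3 then classifies patients as success or recurrence from symptoms and documented tachycardia in follow-up. "Baseline characteristics and procedural variables will be compared between these two groups", using t-tests, Mann-Whitney U tests or Fisher's exact test. The purpose and decision rule follow at once: "in order to identify those variables associated with better mid/long term outcomes. A two-tailed p value <0.05 will be considered statistically significant".

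The variables are neither listed nor limited in number. No multiplicity adjustment is given, the comparison is not labelled exploratory, and Section 14.6 adds no further considerations. Section 6.1 gives the retrospective cohort no follow-up, so only the prospective patients can be classified.

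**The concern.** A descriptive design has no rule for declaring a finding. Section 14.3 supplies one: a variable with p<0.05 counts as associated with outcome. Applied to an open-ended set of variables in 15 patients, one group possibly very small, such a rule tends to fail in three ways. It can name variables that differ by chance, it misses most real differences of moderate size, and it exaggerates the moderate ones that it does catch.

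Section 14.1 says the pilot is meant to lead to a powered multicentre trial. A published list of significant associations could be read as evidence when that trial is designed, and a report of no significant association could be read as evidence of absence. Neither reading would be justified.

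**Working it through.** The plan has no calculation of its own to reproduce: 15 is stated without effect size, power or event rate.

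**Inputs from the documents.** At most 15 patients (Sections 3 and 14.1); two-sided 5% per test and three named tests (Section 14.3); no enlargement from the controls (Section 6.1).

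**Assumptions, because the documents are silent.** 1 to 7 recurrences of 15, no dropout; 10 or 20 variables; true differences of 0.5 to 1 SD.

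**1. False positives, all nulls true.** For k independent tests of exact size 0.05, the chance of at least one is 1 − 0.95^k.
- k = 10: 1 − 0.95^10 = 0.401
- k = 20: 1 − 0.95^20 = 0.642

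These are upper-end figures, because correlation lowers them and Fisher's test runs below its nominal size. With 2 to 4 recurrences and a factor present in 30% or 50% of patients, Fisher's actual size is 0.0009 to 0.0184. If every variable were binary:
- k = 10: 1 − 0.9991^10 = 0.009 to 1 − 0.9816^10 = 0.17
- k = 20: 1 − 0.9991^20 = 0.018 to 1 − 0.9816^20 = 0.31

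A mix of continuous and binary variables falls between.

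**2. Power of one t-test.** Noncentral t, 13 df, noncentrality d·√(n1·n2/15).

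| Recurrence v success | Power, 0.8 SD | Power, 1 SD | Difference for 80% power |
|---|---|---|---|
| 2 v 13 | 16% | 23% | 2.30 SD |
| 3 v 12 | 21% | 30% | 1.96 SD |
| 4 v 11 | 25% | 36% | 1.77 SD |
| 5 v 10 | 27% | 39% | 1.66 SD |
| 7 v 8 | 30% | 43% | 1.57 SD |

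**3. Exaggeration.** At 4 v 11 the observed difference must reach t(0.975, 13)·√(1/4 + 1/11) = 2.160 × 0.584 = 1.26 SD. In 200,000 simulated comparisons, the average significant difference was 1.71 SD when the truth was 0.8 SD (2.1-fold) and 1.65 SD when it was 0.5 SD (3.3-fold).

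**4. Share of significant results that are false.** With a proportion π of variables truly differing by 0.8 SD, the share is 0.05(1 − π) / [0.05(1 − π) + power·π].
- π = 0.1, 3 recurrences: 0.045 / (0.045 + 0.021) = 0.68
- π = 0.3, 5 recurrences: 0.035 / (0.035 + 0.082) = 0.30

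**5. A single recurrence.** The smallest two-sided p is 1/15 = 0.067 for Fisher and 2/15 = 0.133 for Mann-Whitney, so neither can reach 0.05. A pooled t-test of 1 v 14 can, with 15% power at 1 SD and 43% at 2 SD. If the success rate were 75% to 90%, the binomial chance of at most one recurrence in 15 would be 8% to 55%.

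**6. Would adjustment rescue it?** Bonferroni over 10 to 20 variables leaves 2% to 6% power for 0.8 SD with 3 to 5 recurrences. It would not.

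**The case against.** The strongest reply is that this is an unadjusted univariate comparison in a feasibility pilot, supporting none of the endpoints in Section 14.2. Section 14.3 speaks of association, not prediction, and Section 14.1 nowhere says that these associations will inform the later trial. On this view the matter is largely one of labelling. That stands as a limit on the consequence. It does not remove the conflict, because pilot status is the reason for a descriptive design and Section 14.3 departs from it with an explicit threshold and purpose.

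A reader might also infer more than the documents support:

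- *That any significant association would be false, or mostly chance.* The false share is about 30% to 68% under the stated assumptions, so a majority in only part of the range. A very large true difference could be found: at 3 v 12, a 2 SD difference has 82% power.
- *That the rule gives either false findings or none at all.* With one recurrence this fails for the t-test, which Section 14.3 names first. With more recurrences, real differences are sometimes detected.
- *That 40% or 64% is the expected false-positive chance.* It is an upper-end figure, for the reasons in step 1.
- *That the recurrence group will be very small.* The documents give no recurrence rate for this population. Section 4.1 mentions up to 75% success, but for scar-related arrhythmia.

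**Conclusion.** The concern holds in a limited form. Section 14 and the success/recurrence comparison in Section 14.3 conflict, and the sample cannot support the stated purpose. Across the assumed splits, power for a 1 SD difference stays below one half, and 80% power needs roughly 1.6 to 2.3 SD with 2 to 7 recurrences. Moderate effects that reach significance are overstated, about twofold for a true 0.8 SD difference at 4 v 11. Associations named by this rule would therefore generally, though not inevitably, be unreliable.

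The conflict of wording rests on the text alone. The magnitudes rest on assumed recurrence counts, numbers of variables and effect sizes. Because no primary or secondary endpoint depends on the comparison, the consequence is moderate: the change should be made, but the study's main results do not turn on it.

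**What to change.** In Section 14.3, for the success/recurrence comparison only:

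- Remove the aim of identifying variables associated with outcome.
- State that the p<0.05 threshold does not apply to this comparison.
- Present baseline and procedural variables by outcome group as individual values or medians, with differences and 95% confidence intervals labelled exploratory and unadjusted. The label matters, since reading many intervals for whether they exclude zero would bring the same multiplicity back.
- State that no variable will be reported as associated with, or predictive of, outcome on the basis of a significance test.

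The threshold sentence should not simply be deleted. It is the only significance level in Section 14.3, so deletion would also affect the McNemar and Cox analyses there. Whether those analyses fit a descriptive design is a separate question that this change leaves open.

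The cost is a change of wording, with no change to data collection. The report gives up any claim of significant associations with outcome.

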10.4 SUBSEQUENT ASSESSMENTS

Follow-up

3 months (follow-up visit – study completion - endpoints assessment)

The next scheduled follow-up visit after discharge will be at approximately three months post PVC/VT ablation. The following assessments will take place:

- Patient's symptoms (questionnaire) and clinical assessment
- Review of medication
- 12-lead ECG
- 12-lead Holter (Mortara)
- If high PVC/ VT burden at 3 months, either therapy change or repeat ablation (according to patient and physician preference).

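### Section 14.3 sets a within-patient test at a 6-month visit that the 3-month study does not have, and plans a Cox model that one scheduled rhythm check in 15 patients cannot support

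*Combined protocol and SAP*

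**What the plan says.** Section 14.3 contains two analyses at issue.

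- **Within-patient test.** "Intra-patient improvement from baseline to 6 months follow-up visit will be assessed by" McNemar's test. The variable that is to improve is not named. A second McNemar test in the same section relates acute success to outcome and is a separate matter.
- **Cox model.** "Freedom from PVC/VT will be assessed as a time-dependent variable using Cox proportional hazard models". That sentence is the whole specification. It gives no covariate or groups, no event-date rule and no censoring rule.

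Section 14.3 also reports outcome in the entire cohort as the "percentage of patients free from symptomatic or documented arrhythmia or with only mild symptoms related to arrhythmia recurrence".

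On timing, section 6.1 says: "The follow up will be of three months". Section 10.4 says: "The next scheduled follow-up visit after discharge will be at approximately three months post PVC/VT ablation", and labels that visit "study completion - endpoints assessment". The charts in sections 6.3 and 10.5 and in the appendix have no later column. The secondary endpoint in section 14.2.2 is set at 3 months.

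On the historical cohort, section 6.1 says: "For this second retrospective cohort there will be no follow-up". Sections 14.1 and 14.3 nevertheless plan to compare the trial's outcome with matched procedures from the same five-year database.

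**The concern.** An analysis tied to a visit that will not take place cannot be carried out. Someone will have to choose the time point and the variable later, possibly with the data in view.

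The Cox model raises a different problem. It uses the order of event times, and the schedule supplies almost none. Recurrences first found at the 3-month Holter are known only to have arisen at some time before it. The model's comparison, event dates and censoring would all have to be chosen after the fact, and 15 patients can give only a handful of recurrences. Section 14.1 says that the pilot is meant to inform a powered trial, so an unstable hazard ratio would be a poor figure to carry forward.

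**Working it through.** **1. Calendar.** Inputs: recruitment of 6 months (section 14.1: "The estimated recruitment period for the trial will be of 6 months"), follow-up of 3 months (section 6.1), study duration of 9 months (synopsis).

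- Recruitment + follow-up = 6 + 3 = 9 months, which reproduces the stated duration.
- With a 6-month visit: 6 + 6 = 12 months, which does not.
- If recruitment were even over 6 months (an assumption), the share able to reach 6 months by month 9 is (9 − 6)/6 = 0.5, or 7.5 of 15 patients.

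The only other follow-up of 6 months or so is the care after certain serious adverse events in section 12.4. It is not an efficacy visit.

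**2. McNemar's test once the month is corrected.** If the chosen variable is present in every patient at baseline, nobody can worsen and all discordant pairs go one way. With b improvers, the exact two-sided p is 2 × 0.5^b:

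- b = 5: p = 0.0625
- b = 6: p = 0.031

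The p value then only restates the number of improvers. Six of 15 is 40% with an exact 95% CI of 16% to 68%, which is the informative result.

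**3. Cox model: events available.** A model of first recurrence in 15 patients has at most 15 events. For a covariate that splits patients equally, at two-sided 0.05 and 80% power, Schoenfeld's formula gives events = 4 × (1.960 + 0.842)² / (ln HR)². The hazard ratios are assumptions:

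| Assumed HR | Events needed |
|---|---|
| 0.5 | 66 |
| 0.33 | 26 |
| 0.25 | 17 |

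All exceed 15.

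**4. Cox model: precision.** Assume an arbitrary covariate splitting patients 7 and 8, with 3 and 1 recurrences, all found at the same visit time. With Breslow ties the score equation is 4 × 7h/(7h + 8) = 3, so h = 24/7 = 3.43. The standard error of log h is 1/√(4 × 0.75 × 0.25) = 1.155. The 95% CI is 3.43 × exp(±1.96 × 1.155), or 0.36 to 33.

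**5. The 3-month proportion instead.** Exact (Clopper-Pearson) 95% intervals on assumed counts:

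| Case | Result | 95% CI |
|---|---|---|
| 12 of 15 succeed | 80% | 52% to 96% |
| 2 of 15 have no 3-month outcome, 10 of 13 succeed; the 2 excluded | 77% | 46% to 95% |
| Same data; the 2 counted as failures | 67% | 38% to 88% |

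These intervals are wide too, but they describe a quantity that the schedule measures. The last two rows show that the handling of missing outcomes moves the estimate by 10 percentage points.

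**The case against.** The strongest reply is that 6 months is a slip, put right by one word because every scheduled-visit statement says 3, and that section 14 calls the statistical design descriptive only. The first half is probably true. It does not name the McNemar variable or repair the Cox model. As to the second half, section 14.3 itself sets a two-tailed 0.05 threshold and names the tests. The reply does limit how serious the point is.

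A reader might infer more than the documents support:

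- **That the Cox model cannot compare VIVO with control.** Section 6.1 may mean only that no study visits are scheduled for the historical cohort, and sections 14.1 and 14.3 plan an outcome comparison with it. The documents do not say whether the database holds recurrence data. What stands is a conflict that must be reconciled.
- **That the absence of a PVC-burden analysis is an error.** The endpoint in section 14.2.2 can be read as a yes/no response, with the success/recurrence split and the McNemar test as its loosely defined analysis. No section promises a quantitative change.
- **That the success percentage has no denominator or follow-through.** Section 14.3 uses the entire cohort, section 7.3 keeps withdrawn patients in clinic follow-up, and section 13.2 provides for telephoning non-attenders. Only the counting of a missing outcome is unstated.
- **That the dating of recurrences would distort the hazard ratio.** On the assumed data above, different dating moves it between 3.10 and 4.51 (Breslow). That is far inside 0.36 to 33, so the shortage of events is what matters.

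**Conclusion.** The point holds in two parts. First, the baseline-to-follow-up McNemar test is wrong as written: its visit lies outside a 3-month study whose own calendar closes only at 6 + 3 = 9 months, and its variable is undefined. This rests on the documents alone. The acute-success McNemar test does not share the time-point error.

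Second, the Cox model does not suit the data. One scheduled rhythm assessment after discharge gives little timing information, and 15 patients give too few events. The missing specification is a matter of record. The hazard ratios and intervals rest on assumed counts and serve only to show scale; the conclusion does not depend on them.

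The point is worth correcting but limited in reach. These are secondary analyses in an unpowered pilot, and the primary endpoints of safety and procedure time are unaffected.

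**What to change.** In section 14.3:

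- **(a)** Change the time point of the within-patient test to 3 months and tie its binary variable to the secondary endpoint in section 14.2.2. If every patient has the condition at baseline, report the proportion improved with an exact 95% CI in place of McNemar's test.
- **(b)** Replace the Cox model with the proportion meeting section 14.3's own success definition at 3 months, with an exact 95% CI, in the entire cohort. Define mild symptoms on the study's symptom questionnaire. Show patients without a 3-month outcome both excluded and counted as failures.
- **(c)** Reconcile section 6.1 with sections 14.1 and 14.3 on whether follow-up outcome will be compared with the historical cohort.
- **(d)** Optional, and not the correction of an error: describe the paired change in Holter PVC burden where comparable unprovoked recordings exist. Sections 4.3.2a and 10.3 plan to record PVC frequency before ablation, but state no recording duration and do not separate provoked from unprovoked segments.

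Items (a) and (b) need only a wording change; the price of (b) is that there is no time-to-event estimate. Item (c) is a clarification of the text. Item (d) may need a protocol change to specify the pre-ablation recording.
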